## **15. DATA MONITORING/REVIEW COMMITTEE**

Not applicable.

## **16. COMPUTER METHODS**

PRA International will perform all pre-defined statistical analyses after the database is locked. Statistical analyses of efficacy and safety data will be performed using Version 9.1 or higher of SAS® (SAS Institute, Cary, NC 27513).

## 17. CHANGES TO ANALYSES SPECIFIED IN PROTOCOL

The following changes to the analyses as outlined in the Protocol Version 6.0 (Amendment 5), 18 Oct 2016 were as follows:

- Subject Disposition for Part 2 (2a and 2b) was proposed to be presented by Treatment group. However, the presentation will be presented by Parts 2a and 2b.
- The Safety Analysis Set 2 was redefined to include Part 3 (long-term safety); therefore, removed Safety Analysis Set 3 and added Safety Completer Set (SCS) to include subjects who received 8 weeks of lanthanum carbonate treatment from Part 2 or Part 3 of the study as a result of and in response to discussions with PDCO.
- An inconsistency in wording exists between the protocol Synopsis (under the Efficacy Analysis section on pages 29 and 30) and protocol Section 9.10.2 (Secondary Variables, page 80). The Synopsis wording states “For the long-term assessment, efficacy and safety variables will be summarized using the FAS and SAS2, respectively...” whereas the wording in Section 9.10.2 states “For the long-term assessment, efficacy and safety variables will be summarized using the Safety Analysis Set 2 for each visit using descriptive statistics...”. The wording will no longer appear in the text, but the SAP will more closely follow what appears in the protocol Synopsis and summarize long-term variables using the FAS analysis population.

The definitions of the FAS and SAS2 are identical except for a subsequent required assessment (ie, at least 1 phosphate assessment or the completion of at least 1 follow-up safety assessment, respectively). It is unlikely that a subject would complete a follow-up safety assessment without also having at least 1 phosphate assessment. As a result, if there is a difference in the size or quality between these 2 analysis populations it would be negligible and hence no impact on the summaries that will be provided.

- The age group categories that will be summarized within the Demographic and Baseline Characteristics tables has been updated from 2 categories (ie, <12 years and ≥12 years) to 4 categories (<10 years, ≥ 10 to <12 years, ≥12 to <18 years and ≥ 18 years) to account for the ages of all subjects who participated in the study across various versions of the protocol and age group categories that appear in the most recent and up-to-date CRF.
- The age group categories that will be summarized for the “by Age” summary tables for Subject Disposition, Demographic and Baseline Characteristics and Adverse Events have been clarified and now explicitly align with the age groups upon which the primary and secondary endpoints are analysed (≥ 10 to <12 years and ≥12 to <18 years vs. <12 years and ≥12 years).
- The study will enrol at least 32 (rather than 35) subjects who complete 8 weeks of treatment with lanthanum carbonate and are assessable for the primary endpoint.
- The definitions of PP1 and PP2 will only include subjects who have serum phosphate levels above the age-specific KDOQI target (rather than equal to or above).

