## 12. APPENDICES

### APPENDIX 1 PROTOCOL HISTORY

Document	Date	Global/Country/Site Specific
Original Protocol (V 1.0)	11 Apr 2012	Global
Amendment 1.0 (V 2.0)	13 Jul 2012	Global
Amendment 1.0 GER	09 Oct 2012	Country-specific
Amendment 1.0 RUS	25 Apr 2013	Country-specific
Amendment 2.0 (V 3.0)	24 Sep 2012	Global
Amendment 2.0 RUS	28 July 2014	Country-specific
Amendment 3.0 (V 4.0)	17 Apr 2014	Global
Amendment 4.0 (V 5.0)	02 Mar 2015	Global
Amendment 5.0 (V 6.0)	18 Oct 2016	Global

Protocol Amendments		
Summary of Change(s) Since Last Version of Approved Protocol		
Amendment Number: 4.0	Amendment Date: 02 Mar 2015	Global/Country/Site-Specific: Global
Description of Change		Section(s) Affected by Change

Protocol revised to match updated SAP:                      Redefined Full Analysis Set.                      Redefined Safety Analysis Set 3.                      Described subject disposition for all study parts.                      Described summarization methods for demographic and baseline characteristics (updated to align with finalized SAP).                      Described intent for listing and analyzing investigational product exposure.                      Described methods for listing prior and concomitant medication.                      Described safety analyses.
		
Study Synopsis; Section 9.5;                      Section 9.6; Section 9.7; Section 9.8;                      Section 9.9; Section 9.11

Changed coordinating principal investigator to PPD [REDACTED], MD, PhD.
		
Title page; Study Synopsis

Updated study duration to 44 months (extended to 2016).
		
Study Synopsis

Protocol updated to include collection and analysis of local laboratory values for serum calcium, serum phosphorus, and calcium phosphorus product for Visits 3.0 through 3.4.
		
Table 1; Section 7.1.2.7; Section 9.10.2

Clarification of characterization of lab parameters.
		
Section 7.2.3.5

Protocol Amendments		
Summary of Change(s) Since Last Version of Approved Protocol		
Amendment Number:	Amendment Date:	Global/Country/Site-Specific:
3.0	17 Apr 2014	Global
Description of Change		Section(s) Affected by Change
Age range amended from 6 months to <18 years to 10 years to <18 years		Protocol Title; Sections 2.2.2, 3.2, 4.1, 6.2.1, 7.1.2, 7.2.2, 9.10.1; Study Synopsis

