The correction of blood sample volumes for all laboratory and pharmacokinetic samples		Section 7.2.3.5 Clinical Laboratory Evaluations Section 7.2.4.1 Clinical Pharmacology Assessments Section 7.2.5 Volume of Blood to be Drawn From Each Subject
Advice on the use of a catheter for blood sampling has been deleted		Section 7.2.5 Table 4 Volume of Blood to be Drawn From Each Subject

Protocol Amendments		
Amendment Number: 1.0 GER	Amendment Date: 09 Oct 2012	Global/Country/Site-Specific: Country specific
Description of Change		Section(s) Affected by Change
Study physician changed to PPD		Protocol Signature Page
Actions to be taken to minimize discomfort to subjects added		7.0
Restrictions on the maximum amount of blood that can be drawn from subjects during a 4-week period has been included		7.2.5

The publication policy has been updated to state that:
 
 
• The results of the study will be published regardless of whether the study results are positive, neutral, or negative
 
• A publication steering committee will be created to act as a non-commercial body that advises or decides on dissemination of scientific study data
 
• The principal investigator will own (or share with other authors) the copyright on his/her publications
 
• The definition of publication is clarified
 
• The results corresponding to the multicenter study should be published first
 
• Authorship will comply with the current International Committee of Medical Journal Editors standards
 
		10.5
The risk benefit assessment has been added		Appendix 2

Protocol Amendments		
Amendment Number: 1.0 RUS	Amendment Date: 25 Apr 2013	Global/Country/Site-Specific: Country-specific
Description of Change		Section(s) Affected by Change
Changed subject age requirement to children aged $\geq 12$ years to $< 18$ years at the time of consent (formerly children and adolescents aged $> 6$ months to $< 18$ years) and revised text as applicable throughout to comply with a regulatory authority request.		Study Synopsis, 2.2.2, 3.2, and 4.1
Added the statement, "Subjects aged 6 months to $< 12$ years at the time of consent will be recruited from other participating countries."		Study Synopsis, 4.5, 9.3, 9.11, and 9.13

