**Part 2:** An overall summary (**Table 4.2.1.3**) and summary by age group (**Table 4.2.1.4**) of the number of subjects in Safety Analysis Set 2 with TEAEs in Part 2 will be presented, including the number and proportion of subjects with any TEAEs, serious TEAEs, TEAEs related to IP, TEAEs leading to study withdrawal, and TEAEs leading to death. The number of events, incidence, and percentage of TEAEs in each treatment group will be presented by SOC and preferred term (**Table 4.2.2.2**); by SOC, preferred term, and maximum severity (**Table 4.3.1.2**); and by SOC, preferred term, and relationship to IP (**Table 4.3.2.2**). Similar summaries by SOC and preferred term will be produced for SAEs (**Table 4.4.1.2**), for deaths (**Table 4.4.2.2**), and for

TEAEs leading to study withdrawal (**Table 4.4.3.2**). AEs, AEs related to IP, SAEs, AEs leading to study withdrawal, and deaths will be listed (**Listing 7.1, Listing 7.3, Listing 7.4 and Listing 7.5**). TEAEs related to bone disease (preferred terms: adynamic bone disease and long bone fracture) are of special interest and will be summarised by SOC and preferred term for Part 2 (**Tables 4.5.1.2 and 4.5.2.2**) and listed separately (**Listing 7.6**).

**Part 2 and 3 combined (lanthanum carbonate only):** An overall summary (**Tables 4.2.1.5 and 4.2.1.7**) and summary by age group (**Tables 4.2.1.6 and 4.2.1.8**) of the number of subjects in Safety Analysis Set 2 and SCS with TEAEs in Part 2 and 3 combined will be presented. The number of events, incidence, and percentage of TEAEs will be presented by SOC by preferred term (**Tables 4.2.2.3 and 4.2.2.4**); by SOC, preferred term, and maximum severity (**Tables 4.3.1.3 and 4.3.1.4**); and by SOC, preferred term, and relationship to lanthanum carbonate (**Tables 4.3.2.3 and 4.3.2.4**). Similar summaries by SOC and preferred term will be produced for SAEs (**Tables 4.4.1.3 and 4.4.1.4**), for deaths (**Tables 4.4.2.3 and 4.4.2.4**), and for TEAEs leading to study withdrawal (**Tables 4.4.3.3 and 4.4.3.4**). AEs, AEs related to lanthanum carbonate, SAEs, AEs leading to study withdrawal, and deaths will be listed (refer to listings noted above). TEAEs related to bone disease (preferred terms: adynamic bone disease and long bone fracture) are of special interest and will be presented by SOC and preferred term in **Table 4.5.1.3 and Table 4.5.1.4** and by sex and age group in **Table 4.5.2.3 and 4.5.2.4** and will be listed separately. (**Listing 7.6**)

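### The by-age disposition, demographic and AE tables have no column for a dosed child under 10, although the safety sets and FAS carry no age limit

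*SAP*

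**What the plan says.** SAP 17 makes two changes to age grouping, in consecutive bullets.

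The first concerns the age rows of the demographic tables. Two categories, split at 12 years, become "4 categories (<10 years, ≥ 10 to <12 years, ≥12 to <18 years and ≥ 18 years". The reason given is "to account for the ages of all subjects who participated in the study across various versions of the protocol", together with the categories on the current CRF.

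The second concerns the tables split by age. The by-age "summary tables for Subject Disposition, Demographic and Baseline Characteristics and Adverse Events have been clarified" and the bands become "≥ 10 to <12 years and ≥12 to <18 years vs. <12 years and ≥12 years", new scheme first. The reason given is that they "now explicitly align with the age groups upon which the primary and secondary endpoints are analysed".

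SAP 5 repeats the two new bands for all three by-age disposition tables, and SAP 7 repeats them for the by-age demographic tables. SAP 11.1 promises an overall AE summary and a "summary by age group" for each part of the study. It names no bands, so SAP 17 supplies them.

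On who may be in the data, Protocol Appendix 1 records under global Amendment 3.0: "Age range amended from 6 months to <18 years to 10 years to <18 years". Under the 2013 Russian amendment, which limited entry in that country to 12 years and over, it records: "Subjects aged 6 months to $< 12$ years at the time of consent will be recruited from other participating countries".

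**The concern.** The two bullets pull in opposite directions. One widens the age categories so that everybody who took part has a place. The next replaces a pair of bands that covered every age with a pair that covers only 10 to <18. SAP 7 applies both schemes to the same by-age demographic tables: the rows include <10, but there is no column in which that row could be filled.

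The reason given is alignment with the efficacy endpoints. That suits the per-protocol sets, which SAP 21.1 restricts to ages 10 to <18 at consent. It does not suit the safety sets or the FAS, which have no such restriction.

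At stake is age-specific safety in the youngest treated children. Protocol 9.13 says the focus was moved to safety, and Protocol 9.11 commits to summarising TEAEs by age group for the defined safety sets without limiting the ages. Under the bands as written, a treated child under 10 would contribute to no by-age AE column, and a reader adding the columns would not reach the overall count.

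**Working it through.** The point turns on which ages each scheme covers. The plan states no figure to reproduce.

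**Step 1: is there an age condition on the sets?**
- SAS1, SAS2 and SCS (SAP 4.3.1 to 4.3.3): none. Membership depends on dosing, a follow-up assessment, or 8 weeks of lanthanum.
- FAS (SAP 4.4): none. It needs one dose and one phosphate assessment.
- PP1 and PP2 (SAP 21.1): aged 10 to <18 at consent.

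**Step 2: could a child under 10 have entered?** The original protocol is dated 11 April 2012 and Amendment 3.0 is dated 17 April 2014 (Protocol Appendix 1). Between those version dates the global eligibility range began at 6 months. These are document dates; no enrolment dates are given.

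**Step 3: place test ages in each scheme.**

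| Age at consent (years) | Replaced bands (<12, ≥12) | By-age bands now | Demographic categories |
|---|---|---|---|
| 0.5, 5, 9.9 | <12 | none | <10 |
| 10, 11.9 | <12 | 10 to <12 | 10 to <12 |
| 12, 17.9 | ≥12 | 12 to <18 | 12 to <18 |
| 18 | ≥12 | none | ≥18 |

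The replaced bands and the four demographic categories each cover every age. The current by-age bands leave <10 and ≥18 uncovered.

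**Step 4: which tables are affected?**
- Disposition by age: 1.1.1.2, 1.1.2.2, 1.1.3.2.
- Demographics by age: 1.2.1.1.2 (SAS1), 1.2.1.2.2 (SAS2), 1.2.1.3.2 (FAS), 1.2.1.6.2 (SCS). The pharmacokinetic sets are drawn from the safety sets and use the same two bands in SAP 7, so 1.2.1.7.2 and 1.2.1.7.4 follow the same logic.
- TEAE overview by age: 4.2.1.2, 4.2.1.4, 4.2.1.6, 4.2.1.8.
- Bone-disease AEs by sex and age group: 4.5.2.1 to 4.5.2.4, if they use the same bands, which the SAP does not say.
- Not affected: 1.2.1.4.2 (PP1) and 1.2.1.5.2 (PP2).

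**Step 5: how large is the gap?** Let k be the number of dosed children under 10 and N the overall count, and assume nobody is 18 or over. The by-age columns sum to N − k, a shortfall of k/N. The documents give no k. Taking N = 65, the approximate planned enrolment in Protocol 3.2, purely as an assumption (the safety sets may be smaller):
- k = 0: 0/65 = 0%
- k = 1: 1/65 = 1.5%
- k = 3: 3/65 = 4.6%
- k = 5: 5/65 = 7.7%
- k = 10: 10/65 = 15.4%

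**The case against.** The strongest reply is that nothing in the documents shows that a child under 10 was dosed. The four demographic categories are explained partly by the CRF. They also include ≥18, although every eligibility range on record stops below 18 at consent, so a listed category need not be populated. SAP 21.1 shows another route to out-of-range ages: where only the birth year is held, age is imputed from 30 June, and an eligible subject can then compute as under 10 or over 18. All of this stands. It makes the effect conditional but does not repair the rule, which gives such a child no column if one exists.

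The second reply is that no information is lost overall. This also stands. A reader might infer that these children drop out of the safety report. They do not: the overall disposition and AE tables include them, the main demographic tables show a <10 row, and AEs and demographics are listed for all enrolled subjects.

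A reader might also infer that the TEAE overviews are the only age-stratified safety tables. They are not, because the bone-disease AEs of special interest are also tabulated by sex and age group.

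The third reply is that the bands were chosen for a reason: they match the endpoint groups and the current eligibility range. That is a fair reason for PP1 and PP2. It does not carry over to sets that admit every dosed subject.

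Finally, the table shells are in a separate document and may contain a reconciling footnote or total column. That cannot be checked here, so the statement that the columns fail to add up rests on the SAP text alone.

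**Conclusion.** The point holds as a conditional reporting gap. As the SAP is written, a dosed child under 10 belongs to the relevant safety set, and to the FAS if phosphate was assessed, but appears in no by-age column of the tables listed above. Those columns would then fall short of the overall N by the number of such children. That number is not stated and may be zero, in which case there is no effect.

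The documents do not support going further. The version dates of 2012 to 2014 show that under-10s were eligible, not that any were enrolled. The ≥18 gap follows from the same rule but is marginal, since age is taken at consent and eligibility stopped below 18; such a subject would be an eligibility violation or a date artefact. No per-protocol table, primary result or overall safety count changes. This is a minor point of table completeness.

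**What to change.** In the by-age tables for the safety sets and the FAS, use the four age categories that SAP 17 already adopts for the demographic rows. At the least, add a <10 column, and a ≥18 column if anyone falls there. State in SAP 11.1 which bands apply to the AE tables, including 4.5.2.1 to 4.5.2.4. The PP1 and PP2 tables can stay as they are.

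Returning to <12 and ≥12 would also make the columns add up, but it would pool any very young child with 11-year-olds and so tell the reader less. If a check of the data shows that no dosed subject was outside 10 to <18, one sentence saying so is enough and the present bands can stand.

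The cost is an edit to the table shells and a line in the SAP before database lock. It needs no new data and touches no efficacy analysis: a free improvement.

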## **18. DATA HANDLING CONVENTIONS**

### **18.1 General Data Reporting Conventions**

Continuous variables will be summarised using the following descriptive statistics: n, mean, median, standard deviation, minimum, maximum. Categorical and count variables will be summarised by the number of subjects (n) and the percent of subjects in each category. Percentages will be presented as whole numbers.

See Shire Standards for rules on the number of decimal places to present data and p-values.

### **18.2 Derived Efficacy Endpoints**

Not applicable.

### **18.3 Repeated or Unscheduled Assessments of Safety Parameters**

If a subject has repeated assessments before the start of IP, then the results from the final assessment made prior to the start of IP will be used as baseline. If end of study assessments are repeated or unscheduled, the last post-baseline assessment will be used as the end of study assessment for generating descriptive statistics.

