#### **7.1.2.10 End of Part 3 (Visit 3.5: Week 40/ End of Study for Part 2a; Week 32/End of Study for Part 2b; $\pm 1$ Week)**

- A full physical examination including vital signs, weight and height will be carried out.
- 12-lead ECG will be performed.
- Blood samples will be taken for biochemistry, hematology, and biochemical bone markers.
- All females will undergo a serum pregnancy test.
- All AEs and concomitant medication will be recorded.
- Confirmation of dialysis adequacy and dietary advice will be made.
- The primary reason for withdrawal will be recorded, if applicable.
- All returned study medication will be counted and recorded, and compliance calculated.
- An End of Study (EOS) Visit should be performed for all subjects in the study, including those subjects who discontinue early.

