#### **7.2.3.5 Clinical Laboratory Evaluations**

The name and address of the each clinical laboratory used in this study will be maintained in the Investigator's files at each site.

All clinical laboratory assays will be performed according to the laboratory's normal procedures. Reference ranges are supplied by the laboratory and used to assess the clinical laboratory data for clinical significance and out-of-range pathological changes. The Investigator should assess out-of-range clinical laboratory values for clinical significance, indicating if the value(s) is/are not clinically significant or clinically significant. Abnormal clinical laboratory values, which are unexpected or not explained by the subject's clinical condition may be, at the discretion of the Investigator or Sponsor, repeated until confirmed, explained, or resolved as soon as possible.

The following clinical laboratory assessments will be performed:

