### **8.1.5 Clinical Laboratory Evaluations**

A change in the value of a clinical laboratory investigation can represent an AE if the change is clinically relevant or if, during treatment with the investigational product, a shift of a parameter is observed from a normal value to an abnormal value, or a further worsening of an already abnormal value. When evaluating such changes, the extent of deviation from the reference range, the duration until return to the reference range, either while continuing treatment or after the end of treatment with the investigational product, and the range of variation of the respective parameter within its reference range, must be taken into consideration.

If, at the end of the treatment phase, there are abnormal clinical laboratory values which were not present at baseline, further clinical or laboratory investigations should be performed until the values return to within the reference range or until a plausible explanation (eg, concomitant disease) is found for the abnormal clinical laboratory values.

The Investigator should decide, based on the above criteria and the clinical condition of a subject, whether a change in a clinical laboratory parameter is clinically significant and therefore represents an AE.

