## 11.2 Clinical Laboratory Variables

Clinical laboratory data (biochemistry, haematology, and biochemical bone markers) will be summarised by parameter and visit for Part 1 for the Safety Analysis Set 1 (**Tables 4.6.1.1, 4.6.1.2 and 4.6.1.3**, respectively).

Clinical laboratory data (biochemistry, haematology, and biochemical bone markers) will be summarised by parameter, visit and treatment group for Part 2 and 3 for the Safety Analysis Set 2 (**Tables 4.6.2.1, 4.6.2.2 and 4.6.2.3**, respectively). Additionally, summarization will also be performed by parameter and visit for Lanthanum Carbonate for Parts 2 and 3 for the SCS (**Tables 4.6.2.4, 4.6.2.5 and 4.6.2.6**, respectively).

Descriptive statistics (n, mean, standard deviation, minimum, median, and maximum) for clinical laboratory values (in SI units) and changes from baseline at each assessment time point as well as shift tables (in terms of abnormality: low, normal, and high) from baseline to each visit for quantitative variables will be presented for the following clinical laboratory variables for Part 2 and 3 for the Safety Analysis Set 2 (**Tables 4.6.3.1, 4.6.3.2, 4.6.3.3**) and SCS (**Tables 4.6.3.4, 4.6.3.5 and 4.6.3.6**).

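### SAP 18.3 lets a later off-drug repeat, taken mainly because a value was abnormal, replace the End of Study laboratory value

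*SAP*

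**What the plan says.** SAP 18.3 covers repeated or unscheduled assessments of safety parameters. For End of Study, it says that "the last post-baseline assessment will be used as the end of study assessment for generating descriptive statistics". Nothing in the section ties that assessment to the last dose.

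Protocol 8.1.5 describes how follow-up laboratory work arises. If, at the end of the treatment phase, "there are abnormal clinical laboratory values which were not present at baseline", then "further clinical or laboratory investigations should be performed until the values return to within the reference range or until a plausible explanation" is found. The same section has the return to range judged "either while continuing treatment or after the end of treatment with the investigational product". Protocol 7.2.3.5 adds that abnormal values that are unexpected or unexplained may, at the discretion of the investigator or sponsor, be "repeated until confirmed, explained, or resolved as soon as possible".

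The End of Study draw is at Visit 3.5 (Protocol 7.1.2.10): "Blood samples will be taken for biochemistry, hematology, and biochemical bone markers". The same assessments are done at, or as close as possible to, early discontinuation, except after transplantation (footnote c to the schedules of assessments).

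SAP 11.2 reports the laboratory data as descriptive statistics and changes from baseline, and also as "shift tables (in terms of abnormality: low, normal, and high) from baseline to each visit".

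**The concern.** The two documents interact. The protocol produces extra samples mainly in subjects whose end-of-treatment value was abnormal, and one of its two stopping conditions is that the value has become normal. The SAP then takes the last sample. Subjects with normal Visit 3.5 values keep them, while subjects with abnormal values may have theirs replaced by a later one taken after dosing has ended. The resulting tendency is toward no change.

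This matters because safety is the first secondary objective (Protocol 2.2.2, SAP 3.1.2), and the amended study is described as refocused on safety (Protocol 9.13, SAP 2.5). In a small study, one or two replaced values can change a table, and a single replacement can remove the reported minimum or maximum.

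**Working it through.** No figure in the plan measures this rule, so the check is mainly a reading of the texts together.

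1. **Who has a sample after Visit 3.5?** The only planned contact after Visit 3.5 is a telephone call 7-14 days after the last dose (30±7 days after transplantation; Protocol 7.1.3). No routine laboratory sample is scheduled. A later sample is therefore unscheduled, and the reasons the protocol gives for one are those in 8.1.5 and 7.2.3.5, both of which start from an abnormal value.

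2. **Is that sample on drug?** In both schedules of assessments, product is collected at Visit 3.5 and none is dispensed. A repeat after that visit is off drug.

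3. **Which value is summarised?** Under SAP 18.3, the later one.

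4. **Does another scheduled on-lanthanum value remain?**

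| Parameter | Scheduled samples on lanthanum before Visit 3.5 |
|---|---|
| Biochemistry, bone markers | Visit 2.8 (Part 2a) or Visit 2.4 (Part 2b) |
| Phosphorus, calcium and their product (local laboratory) | also monthly, Visits 3.0-3.4 |
| Haematology | none |
| 25-hydroxy vitamin D | none (baseline and End of Study only) |

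For the last two rows, the rule acts on the only scheduled post-baseline value.

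5. **Does another rule offset it?** SAP 11.2 has no worst-value summary and no on-treatment window. The SAP does use such limits elsewhere: the Week 8 phosphate must be an on-treatment record within ±7 days of day 56 (21.1), and an event more than 3 weeks after the most recent product is not treatment-emergent (11.1). Safety laboratory data have no equivalent.

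6. **Illustration of size.** Let q be the share of subjects newly abnormal at Visit 3.5, and f the share of those whose value is replaced by an in-range repeat. The documents give neither; both are assumed.

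- *Shift tables, only if they use the 18.3 value.* Reported share newly abnormal = q × (1 − f):

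| q | f = 0 | f = 25% | f = 50% | f = 75% | f = 100% |
|---|---|---|---|---|---|
| 10% | 10% | 7.5% | 5% | 2.5% | 0% |
| 20% | 20% | 15% | 10% | 5% | 0% |

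- *Means.* If each replaced value moves toward baseline by d on average, and abnormalities are in one direction, the mean change moves toward zero by q × f × d. With q = 10% and f = 50%, that is 0.10 × 0.50 × d = 0.05d.

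**The case against.** Much can fairly be said for the plan.

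- **The follow-up rule is softer than a requirement to repeat until normal.** A reader might infer that the protocol orders exactly that. It does not. Section 8.1.5 says should, accepts a plausible explanation as an end point, and can be met by clinical investigation without a new sample. Section 7.2.3.5 is discretionary. In a dialysis population, follow-up may end with an explained value that is still abnormal, so the replacement is not always a normal value. This stands. It weakens the bias without removing it, because a later off-drug value still replaces the on-drug one.
- **The shift tables are not named.** SAP 18.3 speaks of descriptive statistics, and SAP 11.2 lists shift tables as a separate output. One cannot conclude that the shift tables are distorted, only that the plan does not say which value they use.
- **The replaced values are not lost.** All laboratory results are listed (SAP 11.2, Listing 8.1.2), and changes judged clinically relevant are recorded as adverse events (Protocol 7.2.3.5 and 8.1.5). This also stands, although the adverse event route depends on investigator judgement and the listing is not a summary.
- **The scope is narrow.** Biochemistry and bone markers have an earlier on-lanthanum visit. No hypothesis test and no primary analysis uses this rule.
- **A repeat can be the better value**, for example after a sample or laboratory error. This stands, and the fix must allow for it.

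**Conclusion.** The concern holds as a directional weakness in a stated rule. With no on-treatment or time restriction, SAP 18.3 can substitute an off-drug value, obtained selectively because an earlier one was abnormal, and so pull End of Study descriptive statistics toward no change. The exposure is clearest for haematology and 25-hydroxy vitamin D. Whether the shift tables share it is unstated.

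The size is unknown. It depends on how often values are newly abnormal at Visit 3.5, how often they are repeated to within range, and whether follow-up repeats enter the analysis database. The documents settle none of these.

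Two numerical inferences are tempting and should not be drawn. The first is a count such as three abnormal subjects out of 32 falling to two, one or none. The 32 are subjects completing 8 weeks of lanthanum (SAP 2.5), whereas the laboratory tables use Safety Analysis Set 2 and the Safety Completer Set, with Visit 3.5 at Week 32 or 40 or at discontinuation. The second is to discount the SAP's 80.6% chance of seeing a 5% event. That figure reproduces (1 − 0.95^32 = 80.6%), and halving the visible rate would give 1 − 0.975^32 = 55.5%. But this assumes that the event is a laboratory abnormality seen only at End of Study, that half are overwritten, and that 32 is the right denominator. The documents support none of these assumptions.

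Should-fix: the bias is avoidable at little cost, but it affects one visit row of descriptive safety output.

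**What to change.** Amend the End of Study sentence of SAP 18.3 before database lock, to this effect:

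- The End of Study value is the scheduled Visit 3.5 or discontinuation sample.
- If that sample is missing or invalid (for example, a laboratory or sample error), use the valid sample closest to the last dose within a stated number of days.
- Apply the same value to the descriptive statistics and to the 4.6.3.x shift tables.
- Show later follow-up repeats in the listings only.

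The team must choose and state the number of days. Because a discontinuation sample may itself be taken after the last dose, it would help to list days since last dose beside each End of Study value. A worst on-treatment value summary is an optional addition.

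The cost is a short SAP edit and minor programming, with no new data. Abnormality counts may look less favourable than under the current rule.
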